8.2.1.3 Events Related to Malignant Neoplasm Progression

Clear progression of neoplasia should not be reported as an AE or SAE (unless the investigator considers the progression of underlying neoplasia to be atypical in its nature, presentation or severity from the normal course of the disease in a particular patient). Findings that are clearly consistent with the expected progression of the underlying cancer should not be reported as an adverse event, and hospitalizations due to the progression of cancer do not necessarily qualify for an SAE. In contrast, all deaths including those related to progression of disease and sudden and unexplained death should be reported as an SAE. However, if the progression of the underlying cancer leads to death, the death should be reported as an SAE of "malignant neoplasm progression." If there is any uncertainty about a finding being due solely to progression of neoplasia, the finding should be reported as an AE or SAE as appropriate.

8.2.1.4 Events Not Qualifying as a Serious Adverse Event

The following are not considered SAEs for this study and, therefore, do not need to be reported as SAEs:

- Hospitalization in the absence of an AE (Preplanned or elective hospitalizations): Hospitalization or prolongation of a hospitalization is a criterion for an AE to be serious; however, it is not in itself considered an SAE. In the absence of an AE, a hospitalization or prolongation of a hospitalization should not be reported as an SAE. This is the case in the following situations:
 - The hospitalization or prolongation of hospitalization is needed for a procedure required by the protocol. Day or night survey visits for biopsy or surgery required by the protocol are not considered serious.
 - The hospitalization or prolongation of hospitalization is part of a routine procedure (eg, stent removal after surgery). This should be recorded in the study file.
 - Hospitalization for survey visits or annual physicals. This should be recorded in the study file.
 - In addition, hospitalizations planned before the start of the study, for a preexisting condition that has not worsened, do not constitute an SAE. Visits to the emergency room that do not result in hospital admission are not considered hospitalizations, but may constitute a medically important event.

- Hospitalization of less than 24-hour duration (eg, patient presents to emergency department, but is not admitted)
- Events occurring outside of the safety reporting period: Events that meet the SAE criteria (as outlined in Section 8.2.1.2) and occur after informed consent but before the first dose of study drug, which are considered unrelated to screening procedures.

Note: If there is any doubt about whether an AE constitutes an SAE, the AE is to be treated as an SAE.

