8.2.1.2 Serious Adverse Events

An SAE is an AE that meets at least one of the following conditions described below that occurs at any dose (or after the informed consent is given and prior to dosing if the SAE is related to a protocol-mandated procedure) that include the following:

- Results in death (Note: death is an outcome, not an event). Any event resulting in death during the safety reporting period (Section 8.2.4.2) must be treated as an SAE and reported as such. An event related to a study procedure that occurs after informed consent, but prior to dosing that results in death must also be reported as an SAE.
- Is life-threatening

(wherein a patient is at immediate risk of death as the event occurred). A life-threatening experience does not include an experience that, had it occurred in a more severe form, might have caused death, but rather an experience *as it occurred* that created an immediate risk of death. For example, hepatitis that resolved without evidence of hepatic failure would not be considered life-threatening, even though hepatitis of a more severe nature can be fatal. Similarly, an allergic reaction resulting in angioedema of the face would not be life-threatening, even though angioedema of the larynx, allergic bronchospasm, or anaphylaxis can be fatal.

- Requires inpatient hospitalization (formal admission to a hospital for medical reasons) or prolongation of an existing hospitalization
- Results in a persistent or significant disability (defined as a substantial disruption in a person's ability to conduct normal life functions) or incapacity
- Results in a congenital anomaly or birth defect

• Additionally, important medical events that may not result in death, be life-threatening, or require hospitalization may be considered SAEs when, based on appropriate medical judgment, the events may jeopardize the patient and may require medical or surgical intervention to prevent one of the outcomes listed above. Examples of such events include allergic bronchospasm requiring intensive treatment in an emergency room or at home, blood dyscrasias or convulsions that do not result in hospitalization, or development of drug dependency or drug abuse.

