8.2.1.5 Other Events Reportable to the Sponsor Within 24 Hours

Certain information, although not meeting one of the definitions of an SAE, must be recorded and reported within 24 hours of awareness to the Sponsor. These include the following:

- Overdose (Section 8.1.1). All overdoses are recorded in the appropriate eCRF with or without an AE. If the AE associated with the overdose is an SAE, an SAE form must be submitted.
- Pregnancies with or without an associated AE (Section 8.2.7)

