8.2.4 Adverse Event and Serious Adverse Event Reporting

8.2.4.1 Documentation, Diagnosis, and Elicitation

All AEs and SAEs must be recorded on source documents and collected in the appropriate eCRF. All SAEs must be reported immediately (within 24 hours of learning of the event) to the Sponsor by submitting the SAE reporting form. The contact information for reporting of SAEs can be found on the SAE reporting form.

For patients meeting study eligibility criteria, events that occur after the patient signs informed consent but prior to initiation of study drug, unless due to a protocol-mandated procedure, will be recorded on the Medical History eCRF. If the event is related to a protocol-mandated procedure, it will be recorded on the AE eCRF. Similarly, any AE that occurs after first dose of study drug through 28 days after the last dose of sapanisertib will be recorded on the AE eCRF. Following the safety reporting period, only SAEs deemed related to the study drug need to be reported. If the patient starts a new anticancer therapy prior to the end of the safety reporting period, nonserious AEs and SAEs will no longer be collected.

AEs should be elicited by asking the patient a nonleading question (eg, "Have you experienced any new symptoms since we last spoke or since your last visit?" "Have you

experienced any changes in symptoms since your last visit?"). The existence of an AE may be concluded from a spontaneous report of the patient; from the physical examination during assessments; or from other tests such as laboratory tests, ECGs, or other protocol-specified procedure. Although AEs should be based on the signs or symptoms detected during the physical examination and on clinical evaluation of the patient, a standard medical terminology rather than the patient's own words should be reported as the AE whenever feasible. The investigator, whenever possible, should combine signs and symptoms that constitute a single disease entity into a final diagnosis, if appropriate. As an example, a report of rhinorrhea, nasal congestion, and fever may be reported as upper respiratory tract infection, if that is a reasonable diagnosis.

Each AE must be assessed for duration, severity, seriousness, and causal relationship to the study drug. The action taken with the study drug and the outcome of the event must also be recorded.

Any unanticipated problems must be reported by the investigator promptly to the IRB/IEC.

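### Sections 8.2.1.2 and 8.2.1.4 can give opposite answers on whether an adverse event leading to a formal admission of under 24 hours is an SAE

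*Combined protocol and SAP*

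**What the plan says.** Section 8.2.1.2 gives hospitalization as one of the criteria that make an event serious: "Requires inpatient hospitalization (formal admission to a hospital for medical reasons) or prolongation of an existing hospitalization". The test is admission; length of stay plays no part.

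Section 8.2.1.4 is a list of exclusions, introduced by "The following are not considered SAEs for this study and, therefore, do not need to be reported as SAEs". One item in that list is "Hospitalization of less than 24-hour duration (eg, patient presents to emergency department, but is not admitted". As laid out, it is a separate item and not part of the item on hospitalization in the absence of an adverse event. A sentence within that other item says: "Visits to the emergency room that do not result in hospital admission are not considered hospitalizations, but may constitute a medically important event". The section closes with a tie-break: "If there is any doubt about whether an AE constitutes an SAE, the AE is to be treated as an SAE".

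Expedited reporting depends on SAE status. Section 8.2.4.1 states: "All SAEs must be reported immediately (within 24 hours of learning of the event) to the Sponsor by submitting the SAE reporting form". Section 8.2.1.5 adds events that, "although not meeting one of the definitions of an SAE, must be recorded and reported within 24 hours of awareness to the Sponsor", but the events it names are overdose and pregnancy only.

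**The concern.** An exclusion by length of stay sits beside a definition by formal admission. A site that applies the exclusion literally would not flag a short, toxicity-driven admission as serious. A site that applies the definition would.

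Three things are at stake:

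- **The endpoint.** Seriousness is one of the components of the primary safety endpoint (Table 1 and Section 10.1), and safety feeds the choice between the two dose schedules (Sections 3.1 and 10.5).
- **Expedited reporting.** An event without SAE status does not go to the sponsor within 24 hours, and nothing in Section 8.2.1.5 catches it. Section 11.3 provides no independent data monitoring committee, so safety review rests with the sponsor and the Study Steering Committee (Section 3.1).
- **Consistency.** With approximately 30 sites (Section 3.1), the same clinical event can be classified in two ways. Where the exclusion is followed, the error is towards too few SAEs.

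**Working it through.** The plan states no figure to reproduce. The check is a comparison of the passages, followed by simple arithmetic on how much one event matters.

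**Step 1. Run four cases through both sections.** All concern an event attributed to neither planned care nor expected tumor progression, which Sections 8.2.1.3 and 8.2.1.4 treat separately.

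| Case | Section 8.2.1.2 | 24-hour bullet in Section 8.2.1.4, read literally |
|---|---|---|
| Admitted, stay of 24 hours or more | SAE | Not excluded: SAE |
| Admitted at 18:00, discharged at 12:00 next day (6 + 12 = 18 hours) | SAE | Excluded: not an SAE |
| Emergency visit, not admitted, important medical event | Can be an SAE by medical judgment | Excluded, with no caveat |
| Emergency visit, not admitted, no other criterion met | Not an SAE | Not an SAE |

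The second case is the conflict. The third is a smaller one. The earlier sentence in Section 8.2.1.4 leaves room for an unadmitted emergency visit to be medically important, and Section 8.2.1.2 gives bronchospasm treated intensively in an emergency room as an example. The 24-hour bullet does not repeat that allowance.

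**Step 2. Trace what happens to the second case if it is classed as nonserious.**

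- From first dose to 28 days after last dose, Section 8.2.4.2 collects all adverse events regardless of cause. The event stays in the data with its CTCAE grade and relatedness, but loses the serious flag and the 24-hour report.
- After that period, the same section collects only related SAEs. A related short admission classed as nonserious could then go uncollected.
- It keeps SAE status in either period if it meets another criterion, such as life-threatening, important medical event, or potential Hy's Law case (Section 8.2.1.8), or if the site invokes the any-doubt note.

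**Step 3. Size of one misclassified event.** Inputs from Section 3.1: Group A has 30 patients randomized 1:1, so 30/2 = 15 per dose. Group B has at most 34 randomized 1:1, so 34/2 = 17 per dose. Both groups together give 15 + 17 = 32 per dose.

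- Change in SAE rate = 1/n.
- Per dose, groups pooled: 1/32 = 3.1 percentage points.
- One Group A cohort: 1/15 = 6.7 points.
- One full Group B cohort: 1/17 = 5.9 points.

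The pooled figure fits the dose decision best, because Section 3.1 bases it on cumulative safety in everyone treated at that dose and schedule. Section 10.5 also allows for review within a cohort, so the single-cohort figures are kept. Each figure applies only if the patient has no other SAE. Section 3.1 replaces patients who leave before their first on-treatment tumor evaluation, and those who were dosed stay in the safety population (Section 10.2.3), so the true denominators may be somewhat larger and the shifts smaller. If Group B stops early, the pooled denominator is smaller and the shift larger.

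**The case against.** The strongest defense is that the two sections can be read together. Section 8.2.1.2 equates hospitalization with formal admission, and the bullet's only example is someone who was not admitted, so the drafter may have meant only visits without admission. The next item in the same list, on events outside the safety reporting period, says expressly that it covers events meeting the SAE criteria. The 24-hour bullet has no such words. This stands as a plausible account of intent, but the example only illustrates and does not limit the bullet. The literal reading remains open to a site.

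A reader might go further and infer that the bullet can only serve to remove real admissions, because unadmitted emergency visits are already covered. The documents do not establish that. The sentence on emergency visits sits under the item on hospitalization without an adverse event, so a separate bullet could have been meant to extend the same rule to visits caused by one.

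The any-doubt note is a genuine safeguard, and two sections that disagree may well create doubt. It helps only where a site notices the disagreement; a site reading the exclusion alone may not. The important-medical-event criterion also helps, but by judgment, whereas formal admission is a fixed criterion.

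A reader might also infer that toxicity data are lost altogether, or that the dose comparison is biased. Neither is supported. Within the safety reporting period, type, incidence, severity and relatedness are still captured, and both doses are subject to the same definitions. Nothing in the documents points to a differential error.

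**Conclusion.** The inconsistency is real and should be corrected. For an adverse event leading to formal admission and discharge within 24 hours, the text supports two opposite classifications, and neither the bullet's example nor the any-doubt note reliably settles which applies. The conclusion rests on the bullet being a separate list item, as laid out, and on sites being free to read it literally.

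The consequence is limited. What is at risk is the serious flag and the expedited report, plus possible non-collection of a related event after the safety reporting period. The shift in the SAE rate is about 3.1 points per event for the dose decision at full enrolment, or 5.9 to 6.7 points if a single cohort is examined. The documents do not give the frequency of such stays, so these figures show the leverage of one event and are not an estimate of actual under-counting.

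**What to change.** Reconcile the two sections in one of two ways:

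1. Delete the 24-hour bullet from Section 8.2.1.4. The section already says that emergency visits without admission are not hospitalizations, and it keeps the caveat about medical importance.
2. Retain the bullet but confine it to emergency department visits without formal admission, drop the duration, and carry that caveat into it.

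Either way, the formal-admission criterion in Section 8.2.1.2 then governs admissions caused by an adverse event, whatever the length of stay. The SAE form instructions should be changed to match. The cost is one bullet in an amendment, a few more SAE reports and a slightly higher stated SAE rate. Design, sample size and treatment rules are unaffected.

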8.2.1.5 Other Events Reportable to the Sponsor Within 24 Hours

Certain information, although not meeting one of the definitions of an SAE, must be recorded and reported within 24 hours of awareness to the Sponsor. These include the following:

- Overdose (Section 8.1.1). All overdoses are recorded in the appropriate eCRF with or without an AE. If the AE associated with the overdose is an SAE, an SAE form must be submitted.
- Pregnancies with or without an associated AE (Section 8.2.7)

8.2.1.6 Clinical Laboratory Results as Adverse Events

The investigator is responsible to assess the clinical significance of all laboratory values collected during the safety reporting period (Section 8.2.4.2). Any clinically significant laboratory results should be entered as medical history or AEs, as appropriate, in the appropriate eCRF.

An abnormal laboratory result that is not already associated with an AE is to be recorded as an AE if it meets any of the criteria below:

- Leading to a change in study drug (eg, dose modification, interruption, or permanent discontinuation)
- Requiring a change in concomitant therapy (eg, addition of, interruption of, discontinuation of, or any other change in a concomitant medication, therapy or treatment)
- At the discretion of the investigator should the abnormality be deemed clinically significant

8.2.1.7 Adverse Events Due to a Protocol Mandated Procedure

A protocol-related adverse event is an AE occurring during a clinical study that is not related to the study drug but is considered by either the investigator or the medical monitor (or designee) to be related to the research conditions (ie, related to the fact that a patient is participating in the study). For example, an AE related to a protocol-mandated procedure may be an untoward event occurring during a washout period or an event related to a medical procedure required by the protocol. These are recorded in the eCRF as an AE if nonserious, and as an SAE if serious (Section 8.2.5).

8.2.1.8. Potential Hy's Law Cases

Wherever possible, timely confirmation of initial liver-related laboratory abnormalities should occur prior to the reporting of a potential drug-induced liver injury event. All occurrences of potential drug-induced liver injury, meeting the below defined criteria **must be reported as SAEs** (Section 8.2.5).

Potential drug induced liver injury is defined as the following:

1. ALT or AST elevation $> 3 \times ULN$

AND

2. Total bilirubin $> 2 \times ULN$, without initial findings of cholestasis (for example without elevated serum alkaline phosphatase)

AND

3. No other **immediately apparent** possible causes of ALT/AST elevation and hyperbilirubinemia, including, but not limited to, viral hepatitis, pre-existing chronic or acute liver disease, or the administration of other drug(s) known to be hepatotoxic.

8.2.2 Assessment of Causal Relationship

Medical judgement should be used in determining the cause of the AE by considering all relevant factors such as, but not limited to, the underlying study indication, coexisting disease, concomitant medication, relevant history, pattern of the AE, temporal relationship to the study drug, and/or dechallenge or rechallenge with the study drug. Causal assessment could either be "related" (encompasses possibly related, probably related, or certainly related) or "not related" (encompasses possibly unrelated, probably unrelated, or certainly unrelated). Criteria for determining causal relationship is defined in Table 5.

Related to Study Drug	 Absence of alternative causes (or difficult to assign to an alternative cause). AE follows a strong or reasonable temporal sequence from administration of study drug. AE could not be reasonably explained by the patient's clinical state, concurrent disease, or other concomitant therapy administered to the patient. Occurrence of the AE follows a known response pattern to study drug. The AE is confirmed with a positive rechallenge or supporting laboratory data.
Not Related to Study Drug	 An AE that is clearly due to extraneous causes (eg, concurrent disease, concomitant medications, disease under study, etc.) Occurrence of the AE does not follow a reasonable temporal sequence from administration of the study drug. AE does not follow a known pattern of response to study drug. AE does not reappear or worsen when study drug is restarted. An alternative explanation is likely, but not clearly identifiable.

Table 5: Criteria for Determining Causal Relationship to Study Drug

AE, adverse event.

8.2.3 Assessment of Severity (Intensity)

Severity describes the intensity of a specific AE (mild, moderate, or severe). The particular event may be of relatively minor medical significance (such as severe headache). Severity is not the same as "serious," which is based on patient/event outcome or action criteria.

Investigators will grade the severity of AEs according to CTCAE v5.0. For terms not specified within the CTCAE, the criteria in Table 6 should be used to determine grade.

AE severity should be recorded in the appropriate section of the AE eCRF and in the patient's source documents.

Grade	Intensity or Severity	Clinical Description
1	Mild	Asymptomatic or mild symptoms, clinical or diagnostic observations only; intervention not indicated
2	Moderate	Minimal, local, or noninvasive intervention indicated; limiting age-appropriate instrumental activities of daily living
3	Severe or medically significant	Not immediately life-threatening; hospitalization or prolongation of hospitalization indicated; disabling; limiting self-care activities of daily living
4	Life-threatening	Life-threatening consequences; urgent intervention indicated
5	Death	Death related to adverse event

 Table 6: Criteria for Determining the Severity (Intensity) of an Adverse Event

Source: Common Terminology Criteria for Adverse Events v5.0

8.2.4 Adverse Event and Serious Adverse Event Reporting

8.2.4.1 Documentation, Diagnosis, and Elicitation

All AEs and SAEs must be recorded on source documents and collected in the appropriate eCRF. All SAEs must be reported immediately (within 24 hours of learning of the event) to the Sponsor by submitting the SAE reporting form. The contact information for reporting of SAEs can be found on the SAE reporting form.

For patients meeting study eligibility criteria, events that occur after the patient signs informed consent but prior to initiation of study drug, unless due to a protocol-mandated procedure, will be recorded on the Medical History eCRF. If the event is related to a protocol-mandated procedure, it will be recorded on the AE eCRF. Similarly, any AE that occurs after first dose of study drug through 28 days after the last dose of sapanisertib will be recorded on the AE eCRF. Following the safety reporting period, only SAEs deemed related to the study drug need to be reported. If the patient starts a new anticancer therapy prior to the end of the safety reporting period, nonserious AEs and SAEs will no longer be collected.

AEs should be elicited by asking the patient a nonleading question (eg, "Have you experienced any new symptoms since we last spoke or since your last visit?" "Have you

experienced any changes in symptoms since your last visit?"). The existence of an AE may be concluded from a spontaneous report of the patient; from the physical examination during assessments; or from other tests such as laboratory tests, ECGs, or other protocol-specified procedure. Although AEs should be based on the signs or symptoms detected during the physical examination and on clinical evaluation of the patient, a standard medical terminology rather than the patient's own words should be reported as the AE whenever feasible. The investigator, whenever possible, should combine signs and symptoms that constitute a single disease entity into a final diagnosis, if appropriate. As an example, a report of rhinorrhea, nasal congestion, and fever may be reported as upper respiratory tract infection, if that is a reasonable diagnosis.

Each AE must be assessed for duration, severity, seriousness, and causal relationship to the study drug. The action taken with the study drug and the outcome of the event must also be recorded.

Any unanticipated problems must be reported by the investigator promptly to the IRB/IEC.

Guidance for reporting SAEs is provided in Section 8.2.5.

All patients who experience an AE will be evaluated at appropriate time intervals until the event resolves or stabilizes. At the conclusion of the study, the investigator and medical monitor will assess unresolved AEs and determine if additional follow-up is warranted as described in Section 8.2.6.

All AEs, whether or not related to the study drug, must be fully and completely documented on the AE eCRF and in the patient's clinical record. In addition, any AE resulting in permanent treatment discontinuation must be recorded on the treatment discontinuation eCRF as well as documented in the patient's clinical record. AE terms should include a diagnosis or underlying cause, as available, in preference to listing the individual signs and symptoms. If the diagnosis is not known, the investigator should record each sign and symptom as an individual AE.

